7. GENERAL STATISTICAL CONSIDERATIONS

7.1. Data Handling Conventions

Analyses will be performed using SAS® [SAS Institute 2011] Version 9.3 or higher.

- Summary tables for continuous variables will contain the following statistics: N (number of subjects in the population); n (number of subjects with data); mean; standard deviation; median; minimum; and maximum. Selected statistics may also include a 2-sided 95% normal approximation confidence intervals (CIs) on the mean.
- Summary tables for categorical variables will include: N (number of subjects in the denominator, X); n (number of subjects in the numerator, xx); and percent and will be presented in the format XX (XX.X%), where the percentage is in parentheses. Selected statistics also may include 2-sided 95% CIs for the percent.
- Date variables are formatted as yyyy-MM-dd for presentation.
- The baseline value for a given parameter is the last non-missing value prior to the first dose. A value is considered post-baseline if it is obtained after the first study drug administration.
- Change from baseline is calculated as (post-baseline result baseline result). Percent change from baseline is calculated as (change from baseline/baseline results * 100). If either the baseline or post-baseline result is missing, the change from baseline and percent change from baseline is set to missing as well.
- If days should be converted to months, the divisor of 30.4375 will be used (i.e., Months = Days / 30.4375)
- Data from all study centers will be pooled for all analyses.

Protocol KO-TIP-001

- Study day is defined as calendar date date of first treatment + 1 if the calendar date is on or after the date of first treatment, and calendar date date of first treatment if the calendar date is before the date of first treatment
- Measurements from unscheduled visits will be included in listings, but not summary tables, including laboratory tests performed at the site.
- Listings will be provided of all data collected in the electronic case report forms (eCRF).
- Wherever possible, data will be decimal aligned.
- For continuous variables, the following conventions will be made for significant digits:
 - Mean (xx.xx)
 - Standard deviation (x.xxx)
 - Median (x.xx)
 - Minimum and maximum (xx.x)

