Determination of objective tumor response will be performed by the Investigator according to the Response Evaluation Criteria in Solid Tumors (RECIST) v 1.1 Electronic copies of tumor images may be de-identified of subject's personal information at the clinical sites and collected by the Sponsor to undergo an external independent radiological review if the sponsor deems it necessary for the final assessment of treatment efficacy. Subjects with a solitary site of disease who have experienced a response may be considered for surgical resection. Subjects with a best response of a partial response and residual disease after salvage surgery will be eligible to continue on study therapy. Information on the duration of response to the last prior therapy will be collected.

Upon disease progression, subjects will be followed approximately every 12 weeks for survival until either death or 12 months after accrual in the subject's study cohort has been completed, whichever occurs first. Information on subsequent anticancer therapy will be collected.

All subjects will be followed-up for safety during treatment and for approximately 30 additional days after treatment discontinuation (or until immediately before the administration of another anticancer treatment). Additional safety follow up may be conducted if unresolved toxicity is present at the End of Treatment visit.

NUMBER OF SUBJECTS PLANNED: Up to 75 evaluable study subjects: 18 subjects in Cohort 1, 37 subjects in Cohort 2 (30 HNSCC, 7 other HRAS mutant solid tumor enrolled in Stage 1) and 20 subjects in Cohort 3.

SUBJECT SELECTION:

Inclusion Criteria

For inclusion of a subject in the study, all of the following inclusion criteria must be fulfilled:

- 1. Subject is at least 18 years of age.
- 2. Subject has a histologically or cytologically confirmed diagnosis of non-hematological malignancy for which there is no curative therapy available. *In addition, in France and Korea, Republic of, subject must have a malignancy that has relapsed or is considered treatment failure to standard of care therapy in a multidisciplinary clinical staff meeting.*
 - a. Cohort 1 will enroll subjects with malignant thyroid tumors with HRAS mutations, independently of thyroid histology.
 - b. Subjects with non-hematological HRAS mutant tumors (except malignant thyroid tumors) who met eligibility criteria were enrolled in the first stage of Cohort 2

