5. SAMPLE SIZE DETERMINATION

In Cohort 1 and Cohort 2, a two-stage design will be independently employed for each of these two cohorts. Eleven study subjects will be enrolled for the first stage of study for each cohort; the study will be terminated if one or less response was observed at end of first stage. A two- stage study design will be used in order to minimize the number of study subjects treated if tipifarnib is not efficacious. This design is intended to allow the termination of accrual earlier in case of unacceptably low efficacy observed during the study.

Protocol KO-TIP-001

An additional seven subjects will be enrolled for the second stage. At the completion of two-stage study, the study is considered as failure if there will be three or less responses out of 18 evaluable subjects, indicating the true ORR is 10% or less. If there are four or more responses, the treatment will be considered of further interest indicating the true ORR is higher than 10%.

For this two-stage study design, a null response rate of 10% and alternative response rate of 30% are assumed. It provides 80% power to detect a difference between 10% and 30% ORR at one-sided significance level of 0.087. Using this design, the probability of terminating the study at the end of first stage is 0.697 if the true ORR is 10% or less while the probability of terminating the study at the end of first stage is 0.113 if the true ORR is 30%.

In order to reject the null hypothesis, 4 confirmed response are required in Cohort 1 or Cohort 2. In Cohort 2, upon observation of 4 confirmed responses, enrollment of HRAS mutant HNSCC subjects will continue up to 30 subjects with HRAS mutant HNSCC (10 enrolled in Cohort 2 Stage 1 and 2 combined, plus 20 additional subjects) to further explore the antitumor activity of tipifarnib in this tumor type. No statistical hypotheses will be tested in this extension.

In addition, to allow for the compassionate treatment of a subject with an HRAS mutant salivary gland tumor, Stage 1 of Cohort 2 was expanded to 12 total subjects in Amendment 4.2. The primary hypothesis of the study was met at the time of this amendment and the addition of this subject will not be taken into consideration for the analyses of the primary or interim analyses of the trial.

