8. SUMMARY OF STUDY POPULATION DATA

All data will be summarized by cohort. A subgroup analysis will further summarize data according to HRAS status and albumin levels at baseline (see Section 7.5). A single safety table will be presented by starting dose (600 mg or 900 mg).

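### SAP 7.1 permits normal-approximation 95% CIs on means with no minimum group size; in planned groups of 11 to 20 subjects they would cover about 92.2% to 93.5%

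*SAP*

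**What the plan says.** SAP 7.1 lists the standard statistics for continuous variables: N, n, mean, standard deviation, median, minimum and maximum. It then adds an option: "Selected statistics may also include a 2-sided 95% normal approximation confidence intervals (CIs) on the mean". No other method for a CI on a mean is named, and no minimum group size is attached.

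SAP 8 says of study population data: "All data will be summarized by cohort". SAP 7.5 describes Cohort 2 by Stage 1 and Stage 2 and adds pooled efficacy subgroups. The Protocol synopsis gives the planned cohort sizes, the last number being that of the third cohort: "18 subjects in Cohort 1, 37 subjects in Cohort 2 (30 HNSCC, 7 other HRAS mutant solid tumor enrolled in Stage 1) and 20 subjects".

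SAP 5 gives the stage sizes. For Stage 1: "Eleven study subjects will be enrolled for the first stage of study for each cohort", and later "Stage 1 of Cohort 2 was expanded to 12 total subjects in Amendment 4.2". For Stage 2: "An additional seven subjects will be enrolled for the second stage". The Cohort 2 extension brings the HNSCC subjects to 30: "10 enrolled in Cohort 2 Stage 1 and 2 combined, plus 20 additional subjects".

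**The concern.** A normal-approximation interval uses the multiplier 1.96, as if the standard deviation were known. Here it would be estimated from the same few subjects, and that extra uncertainty is what the t multiplier allows for. Without it, an interval labelled 95% is too narrow, most of all in the smallest groups.

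The SAP takes more care with small samples elsewhere. SAP 9.1 attaches a size condition to the Wilson interval for the response rate, and SAP 9.2 foresees a different estimator of the median when there are few subjects or events. Means have no such safeguard.

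What is at stake is the honesty of the label on a descriptive interval. No trial decision depends on it.

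**Working it through.** **Inputs.** The nominal level is 95%, two-sided, by normal approximation (SAP 7.1), so the multiplier is 1.960. Group sizes come from the Protocol synopsis and SAP 5 and 7.5:

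- Cohort 1: 18. Cohort 3: 20. Cohort 2 as a whole: 37. All HNSCC: 30. All subjects: 75.
- Cohort 2 Stage 1: 11, or 12 after Amendment 4.2.
- Cohort 2 Stage 2: 7 alone, or 7 + 20 = 27 with the extension.
- Stage 2 plus Cohort 3: 27 + 20 = 47 with the extension, or 7 + 20 = 27 without it.

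The stage sizes add to 11 + 7 + 20 = 38 against the planned 37. This makes no difference here: coverage is 94.2% at either size.

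**The plan's own figure.** The only stated figure is the nominal 95%; the documents give no coverage calculation. The z interval reaches 95% when the standard deviation is known or n is large, so the question is how far short it falls at the planned sizes.

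**Formulas.** For normal data with mean m and estimated standard deviation s, the interval is m ± 1.960 × s/√n. Since (m − μ)/(s/√n) follows a t distribution with n−1 degrees of freedom:

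- Actual coverage = P(|t with n−1 df| < 1.960).
- Width of the t interval relative to the z interval = t(0.975, n−1) / 1.960.

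**Worked case, n = 11.** The z half-width is 1.960 × s/√11 = 0.591 s. The t half-width is 2.228 × s/√11 = 0.672 s. The ratio is 2.228 / 1.960 = 1.137. Coverage of the z interval is P(|t with 10 df| < 1.960) = 92.2%, so it misses 7.8% of the time instead of 5%.

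| n | Group | Coverage of z interval | t multiplier | Width ratio t/z |
|---|---|---|---|---|
| 7 | Cohort 2 Stage 2 without extension | 90.2% | 2.447 | 1.248 |
| 11 | Cohort 2 Stage 1 | 92.2% | 2.228 | 1.137 |
| 12 | Stage 1 after Amendment 4.2 | 92.4% | 2.201 | 1.123 |
| 18 | Cohort 1 | 93.3% | 2.110 | 1.076 |
| 20 | Cohort 3 | 93.5% | 2.093 | 1.068 |
| 27 | Stage 2 with extension | 93.9% | 2.056 | 1.049 |
| 30 | All HNSCC | 94.0% | 2.045 | 1.044 |
| 37 | Cohort 2 as a whole | 94.2% | 2.028 | 1.035 |
| 47 | Stage 2 with extension plus Cohort 3 | 94.4% | 2.013 | 1.027 |
| 75 | All subjects | 94.6% | 1.993 | 1.017 |

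Simulation with 200,000 normal samples per size agrees: 90.3% at n = 7, 92.2% at n = 11, 93.4% at n = 18 and 93.5% at n = 20.

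**Sensitivity to skewness.** The documents say nothing about the shape of the data, so a lognormal with log-SD 1 was assumed. Coverage for z and t is then 78% and 83% at n = 7, 81% and 84% at n = 11, and 85% and 87% at n = 20. The t interval is better, but it does not restore 95%.

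**The case against.** The strongest reply is that no affected output can be named. SAP 7.1 allows these intervals for selected statistics only. The continuous summaries that come to mind are number of cycles and dose intensity (SAP 8.4) and vital signs (SAP 10 and 10.4), and the SAP plans no CI for any of them. Adverse event durations get a median, minimum and maximum (SAP 10.1). Which tables would carry a CI on a mean is left to the companion table shells, which are not among the documents. This stands, and it keeps the point small. It does not remove it: wherever the option is used, the method is fixed and the label is wrong at these sizes.

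The one mean-type quantity with a planned 95% CI is the exposure-adjusted adverse event rate in SAP 10.1, the mean number of events per treatment cycle. No method is named there. A reader might take SAP 7.1 as the default, but the SAP does not say so, and a t interval is not obviously suited to event counts.

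A reader might also infer coverage of 90% or lower. The 90.2% figure needs Stage 2 displayed as 7 subjects. SAP 7.5 gives Cohort 2 only two levels, and the extension was already planned when this SAP version was written, so 27 is at least as plausible. Late cycles and the high-VAF subgroups may be smaller than any group above, but the documents give no sizes for them, so no figure can be attached.

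Finally, the skewed example shows that the t interval is only a partial remedy for non-normal variables. That also stands.

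**Conclusion.** The point holds as a minor one. SAP 7.1 permits, without a minimum group size, a CI method whose actual coverage is about 92.2% to 93.5% in the planned groups of 11 to 20 subjects. It is 90.2% only if Stage 2 is shown without its extension, and about 94% or more from 27 subjects upward. These figures assume independent, normally distributed observations, an estimated standard deviation and every planned subject contributing a value.

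It would be wrong to conclude that the trial's main results are affected. The response rate is a proportion with its own interval (SAP 9.1). Duration of response and PFS are summarised by Kaplan-Meier medians (SAP 9.2), and overall survival by a median (SAP 9.3). The stopping and success rules count responses (SAP 5). It would also be wrong to say that the SAP makes normal-approximation intervals mandatory.

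**What to change.** In SAP 7.1, replace the normal approximation with a t-distribution-based interval on n−1 degrees of freedom for any CI shown on the mean of a continuous variable.

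This changes one phrase and uses a standard software option. It needs no new data and alters no decision rule. The price is wider intervals: about 14% at 11 subjects, 8% at 18, 7% at 20 and under 5% from 27 upward. Coverage becomes exactly 95% for normal data and improves, without reaching 95%, in the skewed example.

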7.2. Interim Analyses and Data Monitoring

One or more interim analyses may be conducted. The first interim analysis will be conducted to assess preliminary anti tumor activity in Cohort 2 Stage 1 patients (N=11). At this interim analysis the decision to terminate the study can be made if one or fewer responses are observed. Further interim analyses may be conducted to present the current data without requiring the application of predefined stopping rules.

Interim Analyses to present data will include all events, including but not limited to adverse events, response assessments, and study drug administration, that are recorded in the database (data cut of Sept 30, 2020 and April 10, 2020).

- Adverse Events
 - If stop date is past the cut off date
 - Remove stop date and change to 'Ongoing'
 - Have Action and Outcome = 'Not Recovered/Not Resolved'
 - Duration will be censored at the data cut off of date, death, or end of study, whichever is first
- Con Med Data
 - If stop date is past cut off date, remove stop date and change to 'Ongoing'
- Study Drug Data
 - Remove stop date if past cut off date. 'Last treatment' will be the last treatment prior to or on cut off date.

Protocol KO-TIP-001

- Any other dates past cut off
 - Remove stop date and change to 'Ongoing'
 - Blank out any information not attainable until completion of record

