10.8 Methods of Recording and Assessing Adverse Events

At each trial visit, the subject will be queried on changes in his/her condition. During the reporting period of the trial any unfavorable changes in the subject's condition will be recorded as AEs, whether reported by the subject or observed by the Investigator.

Complete, accurate and consistent data on all AEs experienced for the duration of the reporting period (defined below) will be reported on an ongoing basis in the appropriate section of the eCRF. Among these AEs, all serious AEs must be additionally documented and reported using an Adverse Event Report Form. It is important that each AE report include a description of the event, its duration (onset and resolution dates (/times "/times" to be completed when it is important to assess the time of AE onset relative to the recorded treatment administration time)), its severity, its relationship with the trial treatment, any other potential causal factors, any treatment given or other action taken (including dose modification or discontinuation of the IPs) and its outcome. In addition, serious cases should be identified and the appropriate seriousness criteria documented. Specific guidance can be found in the eCRF completion and monitoring conventions provided by the Sponsor.

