10.1. Adverse Events

Adverse events will be coded using the latest available version of the Medical Dictionary for Regulatory Activities (MedDRA) Version 19.0. Treatment-emergent adverse events are defined as adverse events that start on or after the first dose of study drug and within approximately 30 days of the last administration of study drug. Adverse events will be summarized by the number and percentage of subjects who experienced the event, according to system organ class and preferred term. A subject reporting multiple cases of the same adverse event will be counted once within each system organ class and similarly counted once within each preferred term.

Unless specified otherwise, the denominator for these calculations will be the number of subjects who received at least one administration of tipifarnib, irrespective of the total number of doses or treatment cycles administered. These conventions will be appropriately modified to calculate AE incidence rates separately for each cycle that study therapy is administered. AE incidence rates may also be calculated based on other measures of subject exposure (e.g., total number of treatment cycles administered).

AE durations will be calculated using all TEAEs. For AEs that are still ongoing at the end of study, we will use either death or the last contact date as the end of AE stop date for calculation the duration of AEs. Median, minimum and maximum of AE durations will be reported.

AEs will also be summarized by NCI-CTCAE version 4.03 severity grade and by relationship to study drug. Additional summaries may also be provided for SAEs, and events resulting in the permanent discontinuation of therapy. All AEs will be included in individual subject listings.

An overall view of TEAEs will be provided, which will include the total number of TEAEs, number of subjects with TEAEs, study drug-related TEAEs, Serious TEAEs, study drug-related Serious TEAEs, Grade 3 or higher study drug-related TEAEs, deaths within 30-days of administration of study-drug, and AEs leading to permanent discontinuation of study drug. Additionally, a corresponding overall view of exposure-adjusted AE incidence will be provided, which will present exposure-adjusted incidence rates (calculated as the mean number of events per treatment cycle) with corresponding 95% confidence intervals.

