Summary tables will be provided which present the incidence of TEAEs by SOC and PT; and the incidence of TEAEs by SOC/PT by maximum severity (NCI-CTCAE Grades 1 through 5), overall and by cohort. Corresponding summaries for laboratory-related AEs will also be provided.

A summary of the AE durations for all TEAEs by SOC/PT will be provided.

Summary tables will be provided which present the incidence of study-drug related TEAEs and the incidence of study-drug related TEAEs with severity scores of Grade 3 or higher by SOC/PT.

Protocol KO-TIP-001

Summary tables will be provided which present the incidence of SAEs, the incidence of study drug-related SAEs, the incidence of TEAEs leading to permanent discontinuation of drug, and the incidence of TEAEs by starting dose (600 mg BID versus 900 mg BID), all by SOC/PT.

Summary tables will be provided which present Grade 3 or above chemistry and hematology toxicities by treatment cycle, fatigue (preferred term) by treatment cycle, and gastrointestinal events (SOC) by treatment cycle.

Data on adverse events will be presented in listings.

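### The SAP 7.2 data-cut rule overwrites the AE action field with an outcome term, which corrupts the interim AE listings and puts the count of AEs leading to permanent discontinuation at risk

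*SAP*

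**What the plan says.** SAP section 7.2 governs interim presentations, with cuts named at 10 April and 30 September 2020. Its scope is broad: "Interim Analyses to present data will include all events, including but not limited to adverse events, response assessments, and study drug administration" recorded in the database.

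The AE rule has a trigger and several consequences. The trigger is "If stop date is past the cut off date". The consequences include "Remove stop date and change to 'Ongoing" and "Have Action and Outcome = 'Not Recovered/Not Resolved". Duration is then censored at the earliest of the cutoff, death or end of study. No exception is made for an action taken on or before the cutoff.

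The same section truncates study-drug records at the cutoff. For other records, it blanks only what could not be known until the record was complete.

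Protocol section 10.8 requires each AE report to give, among other items, any treatment or "other action taken (including dose modification or discontinuation of the IPs) and its outcome". Action and outcome are thus two separate pieces of information.

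SAP section 10.1 plans two outputs on discontinuation: an overview row for "AEs leading to permanent discontinuation of study drug" and a table by system organ class and preferred term giving "the incidence of TEAEs leading to permanent discontinuation of drug". It also puts all AEs in listings. SAP section 8.1 separately tabulates the primary reasons for stopping treatment.

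**The concern.** At a data cut, each record should show what was known on the cutoff date. Resetting Outcome for an event that was still open on that date serves this aim. Resetting Action does not, because a withdrawal or dose change made before the cutoff is already a fact.

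The trigger adds a second problem. It depends on a stop date recorded after the cutoff, so information from after the cut decides whether a pre-cut fact is kept.

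What is at stake is safety reporting, which is the trial's secondary objective. AEs causing permanent discontinuation are a named safety measure in protocol section 12.2.2 and have their own outputs in SAP section 10.1. An error there could also set two interim outputs, AE tables and disposition, against each other.

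**Working it through.** The plan states no figure to reproduce. The check is to follow two hypothetical events through the rule and then through each planned output.

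- Event A: onset before the cutoff, study drug permanently withdrawn before the cutoff because of it, stop date recorded after the cutoff.
- Event B: the same in every respect, but no stop date recorded by the time of extraction.

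On the cutoff date the two are identical: open, with drug withdrawn.

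**Step 1, apply SAP section 7.2.** Event A meets the trigger. Its stop date is removed, it becomes ongoing, and both Outcome and Action become the not-recovered term. Event B has no stop date, so the rule does not fire and Action still reads drug withdrawn.

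**Step 2, follow both into the planned outputs.**

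| Output | SAP section | Event A | Event B |
|---|---|---|---|
| TEAE incidence, maximum grade, relatedness, SAEs (if serious), starting dose | 10.1 | Counted | Counted |
| AE duration | 7.2, 10.1 | Included, censored | Included |
| Overview row and table for permanent discontinuation | 10.1 | Lost if derived from AE Action; kept if derived from another field | Counted |
| AE listing | 7.1, 10.1 | Action shows an outcome term; the true action is lost | Correct |
| Dose-modification summary | 8.4 | Unaffected if built from dosing records; undercounted if built from AE Action | Unaffected |
| Reasons for stopping treatment | 8.1 | Not changed by this rule | Not changed |

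**Step 3, size of a possible undercount.** Suppose the discontinuation outputs use AE Action. Let *d* be the number of subjects with an AE leading to permanent discontinuation by the cutoff, *k* the number of those whose every such AE has a recorded stop date after the cutoff, and *N* the number treated. The reported count is *d* − *k* and the rate is understated by *k*/*N*, with 0 ≤ *k* ≤ *d*. The documents give neither *d* nor *k*, so only the range can be stated: from no error to loss of all *d*. If the outputs use another field, the undercount is zero.

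**Step 4, opportunity for the rule to fire.** The SAP is dated 5 January 2021, which is 270 days after the 10 April 2020 cut and 97 days after the 30 September 2020 cut. This shows that later stop dates could have been recorded. It does not measure the exposure window, because no extraction date is given.

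**The case against.** The strongest reply is that this is a drafting slip. The term written into Action can only describe an outcome, and the neighbouring instruction to blank only what was not yet knowable suggests the author had the right principle in mind. An author might also have had a legitimate reason to touch Action, since an action taken after the cutoff should not appear. Both points are reasonable, but neither rescues the text. It names Action explicitly, makes no distinction by date of action, and is what a programmer would implement.

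Several stronger readings are tempting, and the documents do not support them:

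- *Affected AEs disappear from the interim safety tables.* They do not. The record is kept as ongoing, and the incidence, grade, relatedness, SAE and duration summaries do not use Action.
- *Tables of AEs leading to dose reduction or interruption are undercounted.* No such table is planned. Dose modifications are summarised under exposure in SAP section 8.4, with the source field unstated, and study-drug records have their own cutoff rule.
- *The longest-lasting events are selectively removed.* The trigger needs a recorded stop date. Events still unresolved at extraction have none and keep their true action.
- *The discontinuation rate is certainly understated.* The SAP does not say that these outputs derive from AE Action. They could come from the reason for stopping treatment, and the table shells are in a companion document that is not available here.
- *A trial decision is affected.* The stage 1 go/no-go rests on responses, and the later interim presentations carry no predefined stopping rule.

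What stands after all of this is the corrupted listing entry, the dependence on post-cut information, and an unresolved risk to the discontinuation counts.

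**Conclusion.** The rule is wrong as written and should be corrected, although its reach is narrow. Read literally, it replaces a known pre-cutoff action with an invalid value for every AE that has a recorded stop date after the cutoff, and it treats events with the same status at the cutoff inconsistently.

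The effect on the AE listings assumes only that listings showing Action are produced at the cut; the SAP does not set out which outputs each cut contains. The effect on the discontinuation row and table further assumes derivation from AE Action. If that holds, the count falls by an amount that the documents do not allow to be estimated, and it may no longer match the reasons for stopping treatment in disposition.

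The primary response analysis is untouched. SAP section 7.2 confines the rule to interim presentations; the separate convention in SAP section 10.1 for AEs ongoing at end of study concerns only the date used for duration.

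**What to change.** Amend SAP section 7.2 and the related derivation as follows:

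1. Restrict the overwrite to Outcome.
2. Retain any action taken with study drug on or before the cutoff. Apply this to every AE open at the cutoff, whether or not a stop date was recorded later. If the AE record carries no action date, use the study-drug records, already truncated at the cutoff, to date the action.
3. Name in SAP section 10.1 the field from which events leading to permanent discontinuation are derived.
4. At each cut, reconcile that count with the AE-related reasons for stopping treatment in the disposition table, and explain any difference.
5. Check any outputs already produced for the two 2020 cuts for AE records with an outcome term in Action.

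The cost is one or two lines in the SAP and a minor programming change. The programming may need a link between AE and dosing records, because the AE items listed in protocol section 10.8 include onset and resolution dates but no date of action. No new data collection is required if that link can be made.
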